#### Existing Literature:

SD is a characterized by involuntary, random movement of laryngeal muscles causing disruption of fluent speech with strained-strangled voice quality. SD is more prevalent in women [2, 3]. Onset is typically in midlife. There are two types of SD: (a) adductor (AD) typified by uncontrolled vocal fold closure, and (b) abductor (AB) characterized by uncontrolled vocal fold opening. The AD form is more common and typically occurs during the voiced components of speech. SD symptoms are task specific, occurring during speech but not during other phonatory (e.g., prolonging vowels) or non-phonatory tasks (e.g., breathing). SD shares several abnormal neurologic signs with FD of the head, neck and hand. For example, abnormal blink reflexes were observed in SD, torticollis, and blepharospasm [4-7] and abnormal long-latency responses to peripheral nerve stimulation have been observed in SD [8], in blepharospasm and oromandibular dystonia [9]. Recent evidence from our group and the work of others strongly indicate that basal ganglia-related diseases such as Parkinson's disease or certain forms of dystonia are associated with somatosensory and specifically proprioceptive abnormalities that are closely linked to the observed motor deficits [10-21] (for reviews see: [22, 23]). Finally, our own work confirmed that SD as a voice disorder is associated with a deficit in arm kinaesthesia [24] – a finding consistent with results from patients with FD of the head and neck [21].

Neurophysiology behind VTS. It has long been established that VTS can stimulate muscle spindles [25-27] and mechanoreceptors [28] affecting motor behavior and inducing changes in kinaesthesia [29-31]. In general, vibrating the skin at amplitudes of  $\leq 15 \,\mu\text{m}$  is sufficient to activate Ia muscle spindle afferents of superficial muscles, which evokes a contractile response called the Tonic Vibration Reflex [26, 27]. To elicit kinaesthetic illusions, vibration must typically range between 40-100 Hz [32, 33]. Brief vibration to a relaxed muscle typically leads to an increase in muscle tone that can easily be overcome by voluntary phasic innervation [34], while

Page 7 of 27

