#### 5.2 Study Procedures:

Voice assessment. To assess voice quality, participants will perform two voice production tasks. First, they will vocalize the vowels 'ahh' and 'ee'. They will perform each task three times per assessment. Second, they read aloud twenty test sentences. They will repeat these assessments several times during testing (see Fig. 4). The sentence reading task consists of a set of test sentences based on a 20-sentence inventory described by Ludlow et al. as being sensitive to the voice symptoms experienced in SD [2]. Participants will read the sentences at their own comfortable pace and loudness. In addition, participants will rate their perceived effort level of vocalization on an ordinal scale of 0 to 10 (0 being with no effort and 10 being with maximal effort).

Application of laryngeal vibration. Each VTS trial begins with a 10-second rest period, followed by 4 seconds of vocalization. After 2 seconds of vocalization, vibration will set in while the subject continues to vocalize. Thus, each trial has a rest, a vocalization only, and a vocalization + vibration period. Each participant performs 50 trials per set. The timeline of the complete protocol is illustrated in Figure 4. Testing will begin with a pretest voice assessment, followed by two sets comprising the vibration only and vocalization + vibration conditions. The order of the conditions will be counter-balanced between subjects to account for possible order effects. During the vibration only condition, subjects will be silent and are allowed to read for diversion. After each set a 5-min break will be given and fluids will be offered. Voice assessment batteries will be administered after each set. After completion of two sets and final voice assessments are immediately after treatment (Post 2 OFF), and 20 min and 60 min after VTS has stopped (Post 20, Post 60).

Page 13 of 27

Revised: 9/28/2017

#### Deleted: 4

PROTOCOL TITLE: Effect of Short-term Laryngeal Vibration on Voice Quality. Grant title: Feasibility of laryngeal vibration as a treatment for spasmodic dysphonia 01/31/2021

Figure 2 Experimental design for in-person testing.

Usability questionnaire: The last section of study is to ask participants to fill out a questionnaire about the usability of the wearable collar.

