with no effort and 10 being with maximal effort). This concludes the pretest voice assessment (see Fig. 6). Subsequently, participants will apply the laryngeal vibration on themselves as instructed for a period of 10 minutes. A study personnel will instruct the participant for each step of the testing. The voice assessment will be repeated after each set of VTS and twice during the retention period (see Fig. 6) The procedure for remote testing is identical to the in-laboratory visit except it does not include EEG and eye movement recording.

5 min 5 min 10 min 5 min

Figure 6. Experimental design for remote testing.

The recorded voice data will be stored on the voice recorder that was sent to the participant. The voice data are already deidentified. The audio file names do not contain any HIPPA incompliant information. The files names comprise only the subject ID and the session number (i.e prestest, set 1, etc.). Upon completion of the remote testing session, the participant will receive a prepaid shipping label via email. The participant will print the label and send the equipment back to the laboratory, thus there is no shipping cost for the participant

The stored deidentified voice data will be then removed from the voice recorder and will stored separately on a password protected University of Minnesota HIPAA compliant server where in-laboratory testing data is also located.

Usability questionnaire: The last section of study is to ask participants to fill out a questionnaire about the usability of the wearable collar.

5.3 Study Duration:

The study consists of a single session. Total exposure time to vibration will be approximately 30 minutes. Each VTS set will last 20 minutes. There will be 5 minutes breaks between sets. The interspersed, repeated voice assessment will allow to document time-dependent changes in voice quality and cortical activation due to laryngeal vibration up to 60 minutes past VTS application. Total duration of the study will be 115 minutes.

5.4 Individually Identifiable Health Information:

Page 15 of 27

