#### 15.0 Statistical Considerations

#### 15.1 Data Analysis Plan:

Analysis of voice data. Acoustic analysis will follow the methodology described by [50]. Waveform and wide-band spectrograms will be used to identify and measure the duration of the variables. The acoustic signal will be examined for the presence of phonatory breaks and aperiodic breaks. Phonatory breaks are defined as any voiced phonemic segment without sound that is greater than 50ms; the duration of phonatory breaks will be measured. Aperiodic segments will be identified as any voiced phonemic segment that contains non-repetitive cycles that are greater than 50ms; and the duration of the break will be measured. To standardize the duration measures for both phonatory and aperiodic breaks, the sum of the duration of breaks will be divided by the sum of the duration of all voiced segments for each subject. Inter-rater reliability will be measured using Cohen's alpha and intra-rater reliability will use Pearson's r correlation (expected to range between r=.89 to r= .98 according to [50]). For both break types, the absence of phonation or the presence of aperiodicity at the boundary of a syllable or the beginning of a word will not be considered. We will perform a MANCOVA procedure employing all acoustic variables with pre-/posttests as independent factors. If the MANCOVA is significant, separate univariate ANOVAs will be performed on each acoustic variable (dependent) and assessment conditions as a repeated measure (independent) [50]. Appropriate Bonferroni adjustments will account for multiple testing.

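### Does the break ratio in section 15.1 need a stated task and assessment before the pre/post voice test can be trusted?

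*Combined protocol and SAP*

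**What the plan says.** Section 15.1 sums break time and voiced time and takes their quotient: "the sum of the duration of breaks will be divided by the sum of the duration of all voiced segments for each subject". Its only stated exclusion is for breaks "at the boundary of a syllable or the beginning of a word will not be considered". The ratios go into a MANCOVA on pre- and posttests. Univariate ANOVAs follow, with "assessment conditions as a repeated measure (independent" factor). The section opens by adopting the acoustic method of reference 50, whose listed title covers both sustained phonation and reading.

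Section 5.2 describes the assessment: "To assess voice quality, participants will perform two voice production tasks". The first is vocalising two vowels, and here the text adds "They will perform each task three times per assessment". The second is reading twenty sentences, from an inventory described "as being sensitive to the voice symptoms experienced in SD". The remote procedure, also in 5.2, asks for each vowel five times, yet is said to match the laboratory visit apart from EEG and eye-movement recording.

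The Existing Literature part of section 2 states "SD symptoms are task specific, occurring during speech but not during other phonatory (e.g., prolonging vowels"). Section 5.3 gives the purpose of the repeats: "The interspersed, repeated voice assessment will allow to document time-dependent changes in voice quality".

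**The concern.** Read word for word, the ratio is one number per participant over everything voiced. Such a number could not show change over time. Sustained vowels are voiced, so they would enter the denominator although the protocol expects no symptoms in them. The measure would then be diluted by material unrelated to the disorder.

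The dilution would also depend on the mode of testing, because remote participants produce more vowels. Two people with identical speech would get different ratios, and an improvement of the same size would look smaller remotely. The protocol presents this work as the foundation for a later clinical trial, so a misleading absolute effect size could carry forward. An unstated scoring choice could also be made after the results are seen.

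**Working it through.** The documents give no power or effect-size figure on this point, so there is nothing to reproduce. The check asks what pooling would do if it happened.

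**Inputs from the documents (5.2).** Two vowels, three times each in the laboratory: 2 × 3 = 6. Five times each remotely: 2 × 5 = 10. Each participant has a single session (5.3), so one mode applies to all of that person's assessments.

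**Assumed inputs.** Voiced sentence time S = 30 s; vowel length v = 4 s; no breaks in vowels; a fall of 1.5 percentage points in the sentence ratio; within-assessment SD of 2 points. None of these is in the documents.

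**Dilution.** With n vowels, pooled ratio ÷ sentence-only ratio = S/(S + nv).

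- Laboratory: 30/(30 + 24) = 0.556, so 1.5 points reads as 0.83.
- Remote: 30/(30 + 40) = 0.429, so 1.5 points reads as 0.64.
- Remote ÷ laboratory: 0.429/0.556 = 0.77, a 23% difference for identical speech.
- Over S = 20 to 60 s and v = 2 to 6 s, the factor runs from 0.357 to 0.833 in the laboratory and from 0.250 to 0.750 remotely; remote ÷ laboratory runs from 0.70 to 0.90.
- If vowels carry half the sentence break rate, the factors are (30 + 12)/54 = 0.778 and (30 + 20)/70 = 0.714, a difference of 8%.

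**Effect on the paired test.** The standardised effect is mean change ÷ SD of change.

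- Sentences only: SD of change = 2 × √2 = 2.828; 1.5/2.828 = 0.530.
- Pooled, one mode, stable vowel length: numerator and denominator are multiplied by the same factor, so the effect is still 0.530.
- Pooled, equal mix of modes: mean change = (0.833 + 0.643)/2 = 0.738. The SDs are 2.828 × 0.556 = 1.571 and 2.828 × 0.429 = 1.212. Variance = (1.571² + 1.212²)/2 + ((0.833 − 0.643)/2)² = 1.969 + 0.009 = 1.978. The effect is 0.738/√1.978 = 0.525 (0.524 by simulation).
- Cost in sample size of the mix: (0.530/0.525)² = 1.02, about 2%.
- Simulation with each vowel varying independently by 20%: 0.517 in either mode.

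**Which reading the text supports.** A single value per participant cannot enter an analysis with assessment as the repeated factor, so the ratio must be formed at each assessment. On task, the exclusion for syllable boundaries and word beginnings only makes sense in connected speech, and the sentences were chosen for their sensitivity to SD.

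**The case for a change.** The best case for a change is that the task, unlike the assessment, cannot be deduced with certainty. The boundary rule does not remove vowels, and the title of the cited paper covers both tasks. Stable vowel length is also an assumption. If all vowels in an assessment lengthen or shorten together with a 20% coefficient of variation and contain no breaks, the simulated effect falls to 0.47 in the laboratory and 0.44 remotely. A systematic change in vowel length after vibration would bias a pooled ratio. Naming the task would take a sentence.

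Part of this stands: section 15.1 does not restate the task, and the cited method cannot be checked here. But the larger losses need three things at once: pooling, vowels free of breaks, and a large shift shared by all vowels. At half the sentence break rate, the same shift leaves 0.52 in both modes. The documents give no sign of such a shift.

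The instruction to perform each task three times could be stretched to cover the sentences. It follows the vowels and precedes the sentences, so it belongs naturally to the vowels. Even on the other reading, the mixed-mode effect is 0.50.

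Section 15.1 is also silent on whether audio from the vibration trials is scored. In the set with vocalisation, that is 50 × (4 − 2) = 100 s with vibration on. If it is scored as its own assessment condition, the repeated factor already separates it from the pre/post contrast. Any masking by the device is of unknown size, so it gives no measured reason to alter the plan.

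**Conclusion.** The concern does not call for a change. The missing assessment label is ordinary shorthand that the planned analysis resolves. The missing task label is a detail left to a cited method, and analysts can fill it sensibly by scoring connected speech or by scoring each task separately. No section says vowels and sentences are pooled.

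If they were pooled, the absolute ratios would shrink by an amount that differs by mode. The within-participant test would barely move: 0.53 against about 0.52, on the assumed durations and SDs above and with vowel length stable or varying independently between productions. The 23% gap between modes concerns a comparison that section 15.1 does not plan, so it bears on descriptive values only.

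The three-versus-five vowel repetitions do conflict with the statement that the two procedures match. This is a slip in section 5.2, with no shown effect on the planned test.

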#### 5.0 Procedures Involved

#### 5.1 Study Design:

Subjects will perform voice production tasks before, during and after vibration. The subject will wear the collar around their neck. Two lightweight, low voltage, non-invasive surface electrical vibratory motors that are embedded in the wearable collar will be positioned on the skin of the anterior portion of the neck adjacent to the voice box to vibrate the larynx (see Fig. 3 for demonstrating the location of vibrators). Voice production before, during, and after the vibration will be recorded via a microphone for subsequent acoustic analysis on voice quality by speech analysis experts. In addition, during voice production, electroencephalography (EEG) will be recorded with a 64-channel system (Active 2 BioSemi B.V., Amsterdam, The Netherlands or the mobile ANT Neuro EEGO EEG System, Hengelo, The Netherlands) at a sampling frequency of 512 Hz. Subjects will wear a regular head cap arranged in the standard 10-20 configuration (see Figure 1). Four additional external electrodes will be used. Two electrodes will be placed above and below the left eye to detect eye movements. Another two electrodes will be attached on bilateral mastoid processes to serve as reference electrodes. A water-based conductive gel is applied between the electrodes and the skin, which can be cleaned easily with water.

Deleted: Figure 1

Page 12 of 27

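### Section 15.1 checks hand-marked break durations with a statistic that does not exist by that name and with Pearson's r, which cannot see a constant scoring shift; an absolute-agreement measure is needed.

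*Combined protocol and SAP*

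**What the plan says.** The voice outcome is built from durations. Section 15.1 defines the first break type thus: "Phonatory breaks are defined as any voiced phonemic segment without sound that is greater than 50ms". It adds that "the duration of phonatory breaks will be measured", and for aperiodic segments "and the duration of the break will be measured". The analysed variable is a ratio: "the sum of the duration of breaks will be divided by the sum of the duration of all voiced segments for each subject". Section 5.1 sends the recordings "for subsequent acoustic analysis on voice quality by speech analysis experts", so people set the segment boundaries.

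The quality check is one sentence in section 15.1: "Inter-rater reliability will be measured using Cohen's alpha and intra-rater reliability will use Pearson's r correlation". An expected range of r from .89 to .98 follows, taken from a cited acoustic study. It attaches most naturally to Pearson's r, that is, to the intra-rater check.

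The scores then feed the main comparison: "We will perform a MANCOVA procedure employing all acoustic variables with pre-/posttests as independent factors".

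The document names no absolute-agreement coefficient, mean difference or limits of agreement. It does not give the number of raters, the share of recordings scored twice, or what follows if reliability is low. It does not say whether raters are masked to assessment time or in what order recordings are scored.

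**The concern.** Two things in that sentence do not work.

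First, Cohen's alpha is not a standard statistic. It could be a slip for Cohen's kappa (for categories, so not for a duration), Cronbach's alpha (a consistency measure that ignores a constant offset between raters) or Krippendorff's alpha (whose interval form does register a shift). These behave differently, and the text does not settle which is meant.

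Second, Pearson's r measures how closely two sets of readings follow a straight line, not whether they give the same values. A scorer who marks every break longer or shorter on the second reading, by a roughly constant amount or factor, gets the same r.

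The Study Summary describes a single-intervention, pre-post design, and section 5.2 has no sham or untreated condition. No concurrent comparison would therefore absorb a scoring shift that coincided with the later assessments, and the planned check would not reveal it.

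**Working it through.** **The plan's own figure.** The range .89 to .98 is quoted from a cited study without data, so it cannot be reproduced from the documents. The question is what could lie behind an r in that range.

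**Algebra.** For any constant a and any b > 0, corr(X, a + bY) = corr(X, Y). This needs no assumption about the data.

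**Closed-form illustration.** These inputs are assumptions: true ratio t with mean 0.10 and SD 0.06 (variance 0.0036), and independent reading noise with SD 0.01 (variance 0.0001). First reading X = t + noise; second reading Y = k·t + noise.

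- Var X = 0.0036 + 0.0001 = 0.0037
- Var Y = 0.0036k² + 0.0001
- Cov = 0.0036k
- r = Cov / √(Var X · Var Y)
- Absolute agreement = 2·Cov / (Var X + Var Y + d²), with d = 0.10(1 − k). This is Lin's concordance coefficient, which equals the two-reading, single-measure absolute-agreement ICC in large samples.

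| k | Cov | Var Y | r | d² | Agreement |
|---|---|---|---|---|---|
| 1.0 | 0.00360 | 0.003700 | 0.973 | 0 | 0.973 |
| 0.8 | 0.00288 | 0.002404 | 0.966 | 0.0004 | 0.00576/0.006504 = 0.886 |
| 0.7 | 0.00252 | 0.001864 | 0.960 | 0.0009 | 0.00504/0.006464 = 0.780 |
| 0.5 | 0.00180 | 0.001000 | 0.936 | 0.0025 | 0.00360/0.007200 = 0.500 |

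Every r lies inside .89 to .98. The small fall in r arises only because the noise was not scaled with the signal.

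**Other assumed distributions.** Simulated lognormal durations had mean 100 ms, coefficient of variation (CV) 0.3, 0.5 or 1.0, and error set so that r without a shift is 0.89 or 0.98. The whole second score was multiplied by 1.2, 1.5, 0.8 or 0.5.

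- r stayed at 0.89 or 0.98 in every case.
- Starting from 0.98, the ICC at CV 0.3 / 0.5 / 1.0 was 0.82 / 0.91 / 0.95 for +20%, 0.49 / 0.70 / 0.84 for +50%, 0.76 / 0.87 / 0.93 for −20% and 0.25 / 0.44 / 0.65 for −50%.
- For +20% and +50% from the same start, Cronbach's alpha stayed at 0.95 to 0.98, while interval Krippendorff's alpha ranged from 0.34 to 0.95.

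**Through the 50 ms cut to subject totals.** With assumed gamma durations, 15% random error and r of about 0.99 without a shift, r was 0.99 at +20%, +50% and −20%, and 0.97 to 0.98 at −50%. Totals were off by about +23%, +58%, −24% and −59% to −63%.

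**Drift that builds up within the re-scored set.** From 0 to +50%, r falls from 0.98 to 0.91–0.97 (in range), or from 0.89 to 0.83–0.88 (below range). From 0 to +20%, it falls to 0.96–0.98 or 0.88–0.89.

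**When a shift reaches the pre/post change.** If the same factor k applies at both times, the change and its SD are both multiplied by k and the test statistic is unchanged; an additive shift in the ratio cancels. If k = 0.8 applies only to post recordings and nothing truly changed, the mean change is 0.8 × 0.10 − 0.10 = −0.02, an apparent 20% improvement.

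**The case against.** A reader might infer that a scoring shift passes straight into the estimated effect of vibration. The documents do not support that. A reliability re-reading scores one recording twice and is not the pre/post contrast. A bias common to both times cancels or rescales, as shown above. It enters the contrast only through scoring order, unmasked scoring or different raters at different times. On these the plan is silent, so the risk is open but not demonstrated. It also follows that a better coefficient alone would not remove a time-linked bias.

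A reader might also infer that neither named statistic can measure agreement. That is certain for Pearson's r only. If Krippendorff's alpha was meant, it would detect a shift, and kappa would suit the step of judging whether a break is present. For the inter-rater check, what is established is that the statistic is misnamed and cannot be computed as written.

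Three further points stand. The outcome is a ratio, so a stretch affecting breaks and voiced segments equally would largely cancel; a shift in break marking alone would not. The .89 to .98 range is an expectation, with no pass mark or label, so it cannot be said that the plan would certify a shifted scorer as excellent. And at a 20% shift the ICC can still look good (0.93 to 0.95 at CV 1.0), so the mean difference is the more telling quantity. The cited method paper may contain further checks, but the plan states none.

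None of this supplies an intra-rater check that can see a constant shift.

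**Conclusion.** The point holds in a limited form. The inter-rater statistic is not identifiable, and the only intra-rater statistic is blind to any constant shift or scaling. The second statement is algebra. The sizes are illustrative: with mean 0.10, SD 0.06 and noise SD 0.01, a constant 20% to 50% shortening leaves r at 0.97 to 0.94 while agreement falls to 0.89 to 0.50. Neither the shift nor these inputs come from the documents, and the in-range result assumes a roughly constant shift; progressive drift starting from the low end would take r slightly below .89.

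Bias in the pre/post ratio requires, in addition, that the scoring standard tracks assessment time. The plan neither states nor rules this out. The defect is worth correcting because it is definite and cheap to repair; it does not by itself invalidate the voice analysis.

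**What to change.** In section 15.1, replace both statistics with a two-way absolute-agreement, single-measure ICC with its 95% CI, together with the mean difference and limits of agreement between readings. Compute these on the analysed ratios, separately for phonatory breaks and aperiodic segments, and for both inter-rater and intra-rater readings. Use Cohen's kappa only for the presence or absence of a break. Drop the Pearson range as the benchmark. Add that recordings are scored in random order with the assessment time masked; this addresses the route by which a shift could reach the pre/post change, which no reliability coefficient can close.

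The cost is one or two sentences, with no readings beyond the repeat scoring that the reliability check already implies. Reported reliability may look less favourable, markedly so if a systematic shift exists.

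### Set order is counterbalanced, but the section 15.1 ANOVA has no set-order term, which costs some power at the assessments tied to individual sets and leaves them open to bias if the orders end up unequal

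*Combined protocol and SAP*

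**What the plan says.** Section 5.2 has a pretest "followed by two sets comprising the vibration only and vocalization + vibration conditions". On their sequence it says: "The order of the conditions will be counter-balanced between subjects to account for possible order effects". Outcome data are tied to each set: "Voice assessment batteries will be administered after each set". The last assessments come "immediately after treatment (Post 2 OFF), and 20 min and 60 min after VTS has stopped (Post 20, Post 60"). Between sets, "After each set a 5-min break will be given and fluids will be offered".

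Section 5.3 expects voice to move during the session: "The interspersed, repeated voice assessment will allow to document time-dependent changes in voice quality and cortical activation due to laryngeal vibration".

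The voice analysis in section 15.1 has two stages. The first reads: "We will perform a MANCOVA procedure employing all acoustic variables with pre-/posttests as independent factors". No covariate is named. If that test is significant, "separate univariate ANOVAs will be performed on each acoustic variable (dependent) and assessment conditions as a repeated measure (independent"). Neither stage mentions set order, or a first-set/second-set term beside the condition. The EEG analysis has no such term either.

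Section 10.1 plans 20 patients and 20 controls. The documents give no effect size, SD, correlation, alpha level or power.

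**The concern.** Counterbalancing balances the mean; it does not clean the error term. When two orders are run and the model ignores order, whatever differs systematically between the order groups stays in the residual. If the groups are unequal in size, it also enters the estimate.

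What is left over depends on the repeated factor, which section 15.1 does not define.

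- **Factor is assessment time.** Period is then in the model. Post 1 mixes participants who have just had vibration alone with participants who have just vocalized under vibration. Any difference between these conditions becomes noise, and no test compares them.
- **Factor is the set condition.** The comparison is made, but each participant's difference carries the change from first to second set, with a sign that depends on order.

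At stake is power in a group of 20 patients, and protection of the Post 1 and between-condition contrasts if the orders do not stay equal. Section 5.2 gives no method for keeping balance, and section 12.2 destroys the data of participants who withdraw without a rule for restoring it.

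**Working it through.** The plan states no figure that could be reproduced, so the effect sizes below are assumptions shown over a range.

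**Inputs.** From section 10.1, n = 20 patients. Assumed: two-sided 5%; order splits from 10/10 to 14/6; a true effect of 0.66 SD of the within-patient difference, which gives 80% power at n = 20 with nothing extra in the error. All effects are in units of that SD.

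**Model when the factor is the set condition.** The participant's difference between conditions is d = tau + s·pi + e. Here tau is the condition effect, pi the change from first to second set, s = +1 or -1 by order, and e has SD 1. Without an order term:

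- bias = pi·(n1 - n2)/n
- error variance ratio = 1 + pi²·[1 - ((n1 - n2)/n)²]·n/(n - 1)

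At 10/10 the ratio is 1 + pi²·20/19. Power and false-positive rates were simulated.

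| pi | Variance ratio, 10/10 | Power without term | Power with term | False-positive rate without term |
|---|---|---|---|---|
| 0.25 | 1 + 0.0625·20/19 = 1.07 | 78% | 80% | 4.4% |
| 0.5 | 1 + 0.25·20/19 = 1.26 | 72% | 80% | about 3% |
| 1.0 | 1 + 20/19 = 2.05 | 49% | 80% | 0.6 to 0.7% |

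At equal orders the estimate is unbiased and the test is conservative.

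**Unequal orders, same factor.** The multiplier (n1 - n2)/n is 4/20 = 0.2 at 12/8, 8/20 = 0.4 at 14/6, and 4/16 = 0.25 if four of ten are lost from one order only (10/6). False-positive rates without the term, for pi = 0.25, 0.5 and 1.0:

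| Split | Bias | False-positive rate |
|---|---|---|
| 12/8 | 0.2·pi | 4.9%, about 4.5%, 2.9% |
| 10/6 | 0.25·pi | about 5.0%, 4.8%, 3.8% |
| 13/7 | 0.3·pi | 5.4%, 6.7%, 7.5% |
| 14/6 | 0.4·pi | 6.4%, about 9.6%, 16.5% |

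With the order term the rate stays near 5% at every split.

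**Model when the factor is assessment time** (Pre, Post 1, Post 2, Post 20, Post 60). A pure period effect leaves the error variance unchanged (simulated ratio 1.00). If the two conditions differ by c, each participant's change from Pre to Post 1 is shifted by +c/2 or -c/2, so c/2 replaces pi:

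- c = 0.5: ratio 1 + 0.25²·20/19 = 1.07, power about 80% to 78%
- c = 1.0: ratio 1 + 0.5²·20/19 = 1.26, power about 80% to 72%

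At unequal orders, Pre to Post 1 is biased by (c/2)·(n1 - n2)/n relative to the equal-weight average. At 12/8 this is 0.05 or 0.10 SD for c = 0.5 or 1.0. If the difference reverses sign at Post 2, the Post 2 minus Post 1 contrast is biased by twice that in absolute size, 0.10 or 0.20 SD, as the simulation confirms.

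**Cost of the order term when there is no order effect.** Power goes from 80.1% to 79.9% at 10/10, from about 80% to 78% at 12/8, and from about 80% to 73% at 14/6.

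**The case against.** The strongest reply is that the repeated factor is almost certainly time. The Study Summary describes a single-intervention design with pre- and posttest. Section 15.1 speaks of pre- and posttests just before the ANOVA, the assessments in section 5.2 carry time labels, and section 5.3 is about change over time. Period is then already modelled, and no stated objective is to compare the two vibration conditions. This stands. It makes the smaller losses, 2 to 8 points at the assumed differences, the relevant ones, and it makes the condition comparison secondary. It does not remove the pooling of two conditions at Post 1.

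A reader might infer that the omission inflates false positives in general. The documents do not support that. At equal orders the test is conservative, and at 12/8 or 10/6 the rate stays at or below about 5%. Losses alone would reach an imbalance of 0.4 only if about six of ten went from one order and none from the other (6/14 = 0.43). That is hard to expect in one session of 115 minutes with minimal stated risk.

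A reader might also infer that the whole pre-post result is compromised. It is not: Post 20 and Post 60 follow both sets in either order, so a pure period effect does not distort their comparison with Pre.

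Finally, an order term does not cure unequal carry-over across the 5-minute break, while the protocol itself looks for effects up to 60 minutes. That also stands and limits what the condition contrast can show.

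**Conclusion.** The point holds in a limited form. The design has an order factor introduced for a stated purpose, and the analysis does not use it. With equal orders the harm is lost power, not bias: about 2 to 8 points if the factor is time and the conditions differ by 0.5 to 1.0 SD, and about 2 to 31 points (80% to 78% down to 49%) if the factor is the condition and the period effect is 0.25 to 1.0 SD. With unequal orders, contrasts tied to individual sets are biased in proportion to the imbalance; false positives exceed 5% only when it is marked.

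These sizes rest on assumed effects, 20 patients and a 5% two-sided test. The documents allow no estimate of the real period or condition effect, and with small effects the loss is slight. The change is worth making because it costs little at near-equal orders and settles what the repeated factor is.

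**What to change.** In section 15.1, define the repeated factor and replace the one-factor ANOVA. For each acoustic variable, fit a repeated-measures model with participant (random), assessment time point (Pre, Post 1, Post 2, Post 20, Post 60), set order (between-subject) and order x assessment, keeping any patient/control term. Report change from pretest at each time point, averaged with equal weight over the two orders.

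Report the period-adjusted comparison of conditions as secondary: each participant's Post 2 minus Post 1 difference, compared between orders and halved. The two orders have expectations pi + tau and pi - tau, so half their difference is tau. State that this assumes equal carry-over across the 5-minute break.

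This takes a few sentences and no new measurements, provided set order is recorded for everyone. The documents do not say that it is, and the remote procedure describes order only by reference to the laboratory visit. The price is one residual degree of freedom (18 instead of 19) and, if there is no order effect, the power cost shown in the working, which grows with imbalance. Keeping the orders balanced within the patient group limits that cost.
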